3.1.1 Screening Phase

Potential subjects will be identified by clinically indicated fetal echocardiography in the Fetal Heart Program Clinic by one of the investigators ([name] or [name]). Potential subjects will be screened for eligibility at 24-28 weeks GA by a study nurse using the protocol inclusion and exclusion criteria. Subject permission (informed consent) will be obtained prior to any study related procedures being performed.

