5.1.5 Laboratory Evaluations

Maternal Evaluation: As part of routine prenatal care, each mother will undergo clinically indicated testing. The laboratory tests listed below should have been obtained by the referring physician at the initial prenatal care visit. If not previously collected, clinically indicated testing will be completed as standard of care with the timing determined by the clinicians caring for the mother.

Clinical Laboratory Tests:

- Hemoglobin/hematocrit /platelet count (to be repeated in the third trimester-36 weeks).
- Blood type and antibody screen (to be repeated at 24-28 weeks).
- Rubella titer.
- Urine (protein, sugar, blood, leukocyte esterase at each visit).
- Diabetes screen (at 24-28 weeks).
- Hepatitis B surface antigen.
- Hepatitis C antibodies (optional).
- HIV (to be repeated in the third trimester-36 weeks).
- Syphilis test (to be repeated in the third trimester-36 weeks).
- Pap smear.
- Urinary drug screen (as clinically indicated).
- Urine culture.
- Gonorrhea and Chlamydia cultures (to be repeated in the third trimester-36 weeks).
- Group B streptococcus culture (to be obtained at 36 weeks).

Other Evaluation (only if clinically indicated):

- Cytomegalovirus, herpes simplex, toxoplasmosis, and varicella maternal titers, hemoglobin electrophoresis, Tay-Sacks, fragile X, cystic fibrosis and spinomuscular carrier screen, and parental karyotype will be offered to some.
- Screening for chromosomal abnormalities: first trimester screen, Quad screen, non-invasive prenatal testing (NIPT).
- Fetal karyotype (by chorionic villous sampling or amniocentesis).
- Chromosomal or genetic evaluation through maternal serum assessment for free fetal DNA.

Infant Evaluation: As part of routine care, each infant will undergo clinically indicated testing.

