Statistical Analysis Plan
Randomized Trial of Maternal Progesterone Therapy to Improve
Neurodevelopmental Outcomes in Infants with Congenital Heart Disease.

J. [name], Principal Investigator
[name], PhD, ScD, Statistician

ClinicalTrials.gov identifier (NCT number): [NCT02133573](#)

Sponsor: Children's Hospital of Philadelphia

Version Date: 3/7/2022

Design: Randomized phase II 2-arm trial design

Control: Vaginal lubricant, twice a day

Intervention: Vaginal gel, 90mg twice a day

Consort Diagram: Per recommendations. <http://www.consort-statement.org/consort-statement/flow-diagram>

Primary Endpoint

The primary endpoint is the Motor Scale of the Bayley-III at 18 months of age.

Secondary Endpoints (Pre-specified in the protocol)¹

Secondary endpoints pre-specified in the protocol are:

1. Developmental (Bayley-III at 18 months of age)
 - a. Cognitive Scales
 - b. Language Scales
 - c. Fine motor score
 - d. Gross motor score
 - e. Receptive Communication
 - f. Expressive Communication
2. Adherence to study protocol
 - a. Progesterone regime (Average adherence by medication return and by diary)
 - b. Complete pre- and post-natal MRI's
 - c. Complete 18-month neuro-developmental evaluation
3. MRI-based
 - a. Total maturation score (TMS) on Pre-operative MRI
 - b. Brain volumes on Preoperative MRI:
 - i. Whole Brain
 - ii. Cerebellum
 - c. White Matter Injury
 - i. Volume on early post-natal brain MRI
 - ii. Volume on early post-operative brain MRI
 - iii. Volume change from pre-operative to post-operative brain MRI.

‘Secondary’ endpoints (Post Protocol) As clinical practice and research findings regarding progesterone use during pregnancy evolved over the course of accrual to the trial, these new secondary endpoints were identified. They were prespecified prior to closure of the database, and while the principal investigator and research team, other than [name] and [name] (statistical analyst), were blinded. They include;

1. Fetal Variables: Fetal echocardiogram and OB ultrasound Doppler flows (umbilical artery, uterine artery, middle cerebral artery, oligohydramnios, fetal growth restriction (BW < 10th percentile))
2. Maternal Complications: (gestational hypertension, preeclampsia, abruption, , gestational DM, maternal tobacco use, maternal hypothyroidism)

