¹ We anticipate the trial resulting in at least two publications related to endpoints. In advance of seeing the unblinded data we anticipate a publication describing in depth results related to the primary endpoint and adherence. A brief description of key MRI-based endpoints may be included. A second publication will focus on MRI-based endpoints.

3. Impaired maternal-fetal environment (presence of 1 or more of gestational hypertension, preeclampsia, gestational DM, maternal tobacco use, maternal hypothyroidism)
4. Delivery Complications (abruption, post-partum bleeding, DVT/PE, perinatal mood/anxiety disorder, wound complications (infection, breakdown))
5. Postmenstrual age of neonate at time of birth,
 - a. Categorical: born earlier than 37 weeks postmenstrual age (PMA)
 - b. Continuous: PMA
6. Type of Delivery (Vaginal, Elective C-section, Emergent C-section)
7. Birthweight (BW), absolute and as Z-score
8. Placental descriptors: (placental weight (PW), PW < 10th percentile, ratio of BW to PW, presence of infarction, fetal vascular malperfusion, maternal vascular malperfusion, fetal vascular thrombi).
9. Brain growth and development. Trajectories of total and regional brain volumes and TMS from fetal to first post-natal MRI,
10. Post-operative seizures
11. Microhemorrhage and infarction
12. Age at post-operative MRI
13. Operative management variables (Cardiac operation during first admission y/n, age at first operation, cardiopulmonary bypass (CPB) y/n, weight at first operation, Clancy class, , deep hypothermia circulatory arrest (DHCA) time, Total support time (TST), antegrade cerebral perfusion time, need for extracorporeal membrane oxygenation (ECMO), additional operations with CPB, additional TST, additional DHCA)
14. Mortality (in-hospital, on-study and post-study)
15. Length of stay and selected complications for first surgical admission
16. Weight, length and HC at 18 months, absolute and as WHO percentile and Z-score

Intention to Treat Principle Unless otherwise specified, all analyses are conducted on an ‘as-randomized’ basis, irrespective of adherence to treatment. This analysis follows the intention to treat principle pre-specified in the protocol.

Descriptive Statistics (Intention to treat cohort)

1. Analyses will be done for the overall cohort as well as by primary cardiac diagnosis (HLHS, TGA, Other).

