2. Baseline characteristics of mother: Using descriptive statistics (as appropriate, means median, number of subjects, proportion, standard deviation (SD), interquartile range (IQR)) to summarize demographic (Age of mother, race, ethnicity, education level of parents, clinical characteristics of mother) and clinical characteristics (Primary cardiac diagnosis, time to surgery, whether surgery was carried out) of the study cohort overall and by arm. Assess rates of missing data in baseline characteristics.
3. Determine rates of completion of primary endpoint of the study by arm. Describe causes of attrition including death (by arm). Kaplan-Meier plots of time-to-death by arm while on-study.
4. Characteristics of neonate. Type of birth (vaginal, emergency cesarean, planned cesarean), complications of pregnancy, progesterone level in cord blood, postmenstrual age of neonate, birthweight, sex, genetic anomaly, apo-lipoprotein E (*APOE*) genotype
5. Primary & secondary outcomes. These outcomes will be described using summary statistics, and for continuous variables, graphically to visualize the distribution, overall and by arm.

6. Genetic anomalies. The protocol pre-specified inclusion of 22q11 individuals. Additional anomalies as genomic information has evolved will be described. Subjects will be classified as Abnormal, Suspect, or Normal based on examination by a dysmorphologist and genetic testing (WES, microarray, and other clinical testing). Subjects with 22q11 deletions will be classified as Abnormal.

Efficacy Analysis

1. *Primary Endpoint (Motor Scale, Bayley III)*. The analysis will use a two-sided two-sample T-interval (estimation) or T-test (hypothesis testing). The confidence level will be set at 90% and the Type I error at 10%.
2. Normality will be assessed. A transformation, or alternatively a non-parametric test, will be used as appropriate.
3. Sensitivity of results to diagnosis group will be assessed by including diagnosis group as a stratification variable in a linear regression model.
4. *Continuous Secondary Endpoints* using the same analysis as the primary endpoint:
 - a. Cognitive and Language Scales (Bayley III)
 - b. TMS
 - c. Brain volumes
 - d. WMI volumes
 - e. PVL volumes
 - f. Adherence to study drug

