 - a. In sensitivity analyses, multiple imputation will be used to impute missing outcome data using baseline covariates. Results will be compared to the primary analysis using the complete data.
 - b. Some subjects will have missing data for the 18-month endpoint due to truncation by death. In sensitivity analyses, we will assess the impact of this source of missingness using principal stratification.
9. Subgroup analyses of Primary & Pre-specified Secondary Endpoints:
10. Primary cardiac diagnosis
11. With versus without 22q deletions
12. With versus without any genetic anomaly
13. Males versus Female infants
14. Subjects undergoing surgical repair or not
15. With/without impaired maternal-fetal environment as defined above

Safety Analysis

All subjects the study at will be included in the safety analysis. The frequencies of adverse event (AE) by type, body system, severity and relationship to study drug will be summarized for both the mother and the neonate. Serious adverse events (SAE), if any, will be described in detail. AE incidence will be summarized along with the corresponding exact binomial 95% two-sided confidence intervals.

Further analyses anticipated for additional paper(s)

Using linear regression, we will assess the association between the neurodevelopmental outcomes with:

- 1) MRI findings (microhemorrhage, gray and white matter volumes, white matter injury (WMI) presence and volume, infarction, volume and growth trajectory) to neurodevelopmental (ND) outcomes
- 2) post-operative seizures
- 3) maternal complications and baseline clinical variables including diabetes, hypertension, smoking status, pre-eclampsia, hypothyroidism
- 4) placental findings
- 5) impaired maternal-fetal environment

Using regression techniques, including logistic regression for white matter injury (WMI) and competing risk time-to-event analyses (length of stay) with death as a competing risk), we will assess the association between the outcome (WMI, length of stay) and

- 1) maternal complications and baseline clinical variables
- 2) placental findings
- 3) trajectories of brain growth

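### SAP post-protocol endpoint 3 (impaired maternal-fetal environment) counts traits naturally present before randomisation as events, which shrinks any difference between arms

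*SAP*

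**What the plan says.** In the SAP section on post-protocol 'Secondary' endpoints, the text says that "these new secondary endpoints were identified" during accrual. Item 3 of that list is "Impaired maternal-fetal environment (presence of 1 or more of gestational hypertension, preeclampsia, gestational DM, maternal tobacco use, maternal hypothyroidism". Item 2, Maternal Complications, names the same conditions plus abruption and ends with "gestational DM, maternal tobacco use, maternal hypothyroidism". It is a plain list, with no statement that any one of its entries makes a mother positive. Neither item has an onset rule.

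For primary and secondary outcomes, SAP Descriptive Statistics item 5 states: "These outcomes will be described using summary statistics, and for continuous variables, graphically to visualize the distribution, overall and by arm". Efficacy Analysis item 5 gives binary secondary endpoints an exact confidence interval and Fisher's exact test at a 10% Type I error. The examples named there do not include items 2 or 3.

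On timing, Protocol 3.1.1 states: "Potential subjects will be screened for eligibility at 24-28 weeks GA by a study nurse". Treatment follows from then to 39 weeks. Protocol 5.1.5 lists "Diabetes screen (at 24-28 weeks" weeks of gestation. Smoking and medical history are data elements of the pre-natal record review in Appendix 1.

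The composite has two other uses in the SAP: as a subgroup factor ("With/without impaired maternal-fetal environment as defined above") and as a predictor of neurodevelopmental outcome in the further analyses.

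**The concern.** An endpoint compared between randomised arms should consist of events that treatment could have influenced. A condition already present at randomisation cannot be an effect of the gel. Because one component is enough, a mother who smokes or is hypothyroid at entry is positive on day one, and preeclampsia arising later does not change her status. She adds to the event count in both arms and tells the reader nothing about treatment.

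Two things follow. A real difference in new hypertension, preeclampsia or diabetes, in either direction, is muted in the composite. A chance imbalance in smokers between two small arms also appears as a difference in an outcome. The trial is meant to inform a larger multi-institutional study, so a muted or spurious maternal finding on this composite could be carried into that design.

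**Working it through.** **Check of method against the plan's own figure.** No figure is given for this endpoint. The nearest is the pre-surgical row of Protocol 6.4, Table 2: 19.0% against 8.5% with 60 per group. The 90% interval is 0.105 ± 1.645 × √[(0.19×0.81 + 0.085×0.915)/60] = 0.105 ± 0.102, which is (0.3%, 20.7%), as printed.

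**Inputs from the documents.** Allocation is 1:1 (Protocol 3.2.1). Enrolment is 110-130, so 55-65 mothers per arm (Protocol 6.4); 60 is used below. Type I error is 10% (SAP Efficacy Analysis item 5), taken as two-sided because the SAP says so only for the t-test.

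**Assumptions, not in the documents.** b is the share of mothers already positive at randomisation, equal in the two arms and independent of later events. New-onset risks are 15% and 30%.

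**Formulas.** Observed composite risk = b + (1 - b)p, where p is the new-onset risk. The difference between arms is therefore (1 - b)(p₂ - p₁), and the risk ratio moves towards 1. With π₁ and π₂ the composite risks and π their mean, power = Φ{[(π₂ - π₁) - 1.645√(2π(1 - π)/n)] / √[(π₁(1 - π₁) + π₂(1 - π₂))/n]}.

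**Worked case, b = 20%.** 0.20 + 0.80×0.15 = 0.32, and 0.20 + 0.80×0.30 = 0.44. The difference is 0.12 = 0.80 × 0.15. Power = Φ[(0.12 - 1.645×0.0886)/0.0879] = Φ(-0.293) = 0.385.

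| b | Composite risks | Difference (points) | Risk ratio | Power, normal approximation | Power, Fisher's exact |
|---|---|---|---|---|---|
| 0 (new-onset only) | 15.0% vs 30.0% | 15.0 | 2.00 | 63% | 55% |
| 10% | 23.5% vs 37.0% | 13.5 | 1.57 | 49% | 41% |
| 20% | 32.0% vs 44.0% | 12.0 | 1.38 | 38% | 33% |
| 25% | 36.25% vs 47.5% | 11.25 | 1.31 | 35% | 31% |

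At 55 per arm, power falls from 60% (b = 0) to 36% (b = 20%); at 65 per arm, from 66% to 41%. The number per arm for 80% power rises from 95 to 202 at b = 20%.

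**Other direction.** New-onset risks of 20% on control and 10% on treatment, with b = 20%, become 36% and 28%. The risk ratio moves from 0.50 to 0.78, and power at 60 per arm falls from 0.455 to 0.239.

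**Chance imbalance.** With b = 20% and 60 per arm, the standard error of the difference in baseline share is √(2×0.2×0.8/60) = 7.3 points. A gap of 10 points or more is 0.10/0.073 = 1.37 standard errors, a two-sided probability of about 17%. The test allows for such noise, but a new-onset definition would not contain it at all.

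**The case against.** The strongest case on the other side is that this is a labelling matter in an exploratory list, and that maternal harms are covered elsewhere. Much of it stands.

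- **Item 2.** A reader might infer that Maternal Complications is diluted in the same way. The documents do not support that. It is a list with no pooled definition. Reported singly, its hypertension, preeclampsia and diabetes rows remain visible; its tobacco and hypothyroidism rows are baseline traits placed among outcomes.
- **Maternal safety.** A reader might infer that these items are the only place where harm to mothers would show. They are not. The SAP Safety Analysis tabulates adverse events for mother and neonate, and item 4 lists delivery complications, including abruption. Protocol 8.4 removes hospitalisation for pregnancy-induced hypertension from the serious category, but not from adverse event recording.
- **The SAP's own grouping.** It is tempting to say that the SAP itself calls smoking and hypothyroidism baseline. Its phrase is "maternal complications and baseline clinical variables including diabetes, hypertension, smoking status, pre-eclampsia, hypothyroidism". That heading is mixed and includes pre-eclampsia, so it does not settle which entries are baseline.
- **The test.** No test is expressly assigned to item 3. What clearly applies is description by arm; Fisher's test applies if the list of binary outcomes is read as open-ended. The same post-protocol list also holds plain descriptors such as age at post-operative MRI.
- **Baseline table.** Maternal clinical characteristics are to be summarised by arm, so an imbalance in smokers could be noticed if smoking is among them.

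None of this changes the composite. Its definition is explicit, it is called a secondary endpoint, and secondary outcomes are set out by arm.

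**Conclusion.** The point holds for item 3 and should be corrected, as a modest matter. The direction and the factor (1 - b) follow from the definition alone. The size does not: b and the event rates are assumptions. Across b of 10% to 25%, a true doubling from 15% to 30% shows as a risk ratio of 1.57 to 1.31, with power at 60 per arm of 49% to 35% instead of 63%. Even the new-onset version is not well powered, so the gain is a cleaner estimate rather than a decisive test.

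Onset before randomisation is the natural reading for tobacco use and hypothyroidism, though the documents do not state it. For gestational diabetes it is only possible: screening and enrolment share the same weeks, and neither is said to come first. For gestational hypertension and preeclampsia it is likewise only possible. A reader should not infer that the primary endpoint, the protocol-specified secondary endpoints or the adverse event analysis is affected; none of them uses this composite as an outcome.

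**What to change.** In the SAP, define the item 3 arm comparison as one or more of gestational hypertension, preeclampsia and gestational diabetes first diagnosed after randomisation. Put tobacco use, hypothyroidism and any component already present at randomisation in the baseline table by arm, and move the tobacco and hypothyroidism entries of item 2 there too. Keep the five-condition composite, under a separate name, for the association analyses only. The subgroup line refers back to the same definition, so it should then state its own, based on status at randomisation.

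The cost is a few lines of SAP text and fewer composite events. Some charts will need re-checking: Appendix 1 lists pregnancy complications, smoking and medical history, but no onset or diagnosis dates. The dated record of maternal medication from 30 days before screening (Protocol 4.3) would help to identify treated hypothyroidism that was already present.

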3.2 Allocation to Treatment Groups and Blinding

3.2.1 Randomization

The study biostatistician, [name], will generate a block randomization schedule based on stratification by fetal CHD diagnosis: TGA, HLHS, and other CHD. The randomization schedule will be based on equal allocation of subjects to the progesterone and placebo arms within each block. To ensure blinding, the randomization schedule will be generated using variable block sizes. Upon confirmation of eligibility in the DMS, the randomization module will be programmed to generate a randomization number that corresponds to a unique kit number of progesterone or placebo treatment. This kit number will be used to distribute treatment.

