5. *Binary Secondary Endpoints* will use an exact binomial confidence interval to estimate differences between groups and will be tested using Fisher's Exact test. The confidence level will be set at 90% and the Type I error at 10%. Binary outcomes include
 - a. Presence of WMI pre- and post-operatively
 - b. Completion of MRIs
 - c. Completion of Bayley III at 18 months
6. *Per Protocol and As Treated*
 - a. The analyses of the primary and secondary endpoints described above will be repeated with alternatives to the intention to treat cohort.
 - b. A 'strict' *per protocol* analysis will be used, considering only those subjects who were eligible for the study and who received the treatment as specified in the protocol. This analysis will consider only those subjects who completed at least 90% of their doses at the time of study-based discontinuation (pre-planned at XX weeks or due to earlier labor and delivery). Adherence will be measured in two ways (1) number of medication doses returned and (2) mother's diaries of medication use. Differences in the two measures of adherence will be described.
 - c. As a sensitivity analysis, a 'relaxed' *per protocol* analysis will follow (a) but use completion of 80% of doses instead of 90% of doses, as the cut-off.
 - d. An *as treated* analysis will consider subjects based on their 'dose of progesterone' based on their assignment to control or intervention arm, as well as adherence to study drug in the progesterone arm. In this case we will include dose as a continuous covariate in a regression model, using linear regression for continuous outcomes or logistic regression for binary outcomes. We will assess interactions between dose and treatment arm. This analysis will estimate the effect of the treatment intervention conditional on different levels of adherence to study medication.

7. *Modeling to Adjust for Covariate Imbalance.* Linear or logistic regression analyses of the primary and secondary outcomes will be carried out with adjustment for baseline covariates of fetal brain maturation and development. The covariates will include type of CHD (primary cardiac diagnosis), race, ethnicity, maternal education and socioeconomic status, presence of 22q11 deletions, other identified genetic anomalies and (*APOE*) genotype.
8. Missing data and truncation by death

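### Allocation is stratified by CHD diagnosis but the primary Motor comparison is an unadjusted t-test; leading with the already planned stratum-adjusted model, and using the baseline fetal MRI for TMS and brain volumes, would gain precision at little cost

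*SAP*

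**What the plan says.** Protocol 3.2.1 and 9.1.1 describe a "block randomization schedule based on stratification by fetal CHD diagnosis: TGA, HLHS, and other CHD", with equal allocation within each block.

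The primary Motor analysis ignores those strata. The protocol synopsis, protocol 6.3.2 and SAP Efficacy Analysis item 1 all give the same method: "The analysis will use a two-sided two-sample T-interval (estimation) or T-test (hypothesis testing". If normality fails, item 2 says: "A transformation, or alternatively a non-parametric test, will be used as appropriate". Item 4 analyses the continuous secondary endpoints, including Cognitive, Language, TMS and brain volumes, "using the same analysis as the primary endpoint".

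Diagnosis does appear in supporting roles:
- SAP item 3: "Sensitivity of results to diagnosis group will be assessed by including diagnosis group as a stratification variable in a linear regression model".
- SAP item 7: "Linear or logistic regression analyses of the primary and secondary outcomes will be carried out with adjustment for baseline covariates". On the list: "The covariates will include type of CHD (primary cardiac diagnosis), race, ethnicity, maternal education and socioeconomic status", followed by genetic factors.
- Primary cardiac diagnosis is listed under "Subgroup analyses of Primary & Pre-specified Secondary Endpoints".
- Protocol 6.3.2 has secondary models of TMS, VMWM, Cognitive and Language that include type of CHD.

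A fetal brain MRI is planned before randomisation (protocol abstract), and its analysis yields a fetal maturation score and brain volumes (protocol 5.2.4). Neither is named as a covariate in SAP item 7 or protocol 6.3.2. In the SAP the fetal scan values serve only the post-protocol endpoint on brain-growth trajectories.

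**The concern.** Stratified allocation largely balances diagnosis between the arms. If diagnosis predicts the Motor score, the difference in means varies less than the two-sample standard error assumes, because that standard error still includes the between-stratum variance. The interval is then wider than it needs to be and the test rejects less often than its nominal 10%. Nothing is biased and false positives are not inflated.

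This matters because protocol 6.4 states no power. The trial is justified by how precisely it estimates the Motor difference for planning a pivotal trial. If the strata are prognostic, the headline result would be the less precise of two analyses already in the SAP.

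TMS and brain volumes have a second, separate opportunity: a pre-treatment measurement of closely related quantities is collected but not used to reduce residual variance.

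**Working it through.** **Inputs.** From protocol 6.4: Motor SD 15, 40 evaluable per arm, clinically relevant difference 6.0 points, TMS SD 1.32, 60 per arm for the post-natal MRI, enrolment 110–130. From the SAP: 90% confidence, 10% two-sided type I error. Assumed, because the documents give no value: the share R² of Motor variance explained by stratum, and the correlation between fetal and post-natal TMS.

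**1. The plan's own figure.** Half-width = t(0.95, 2n−2) × SD × √(2/n). For n = 40: t(0.95, 78) × 15 × √(2/40) = 5.58, which matches the 5.6 in Table 1.

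**2. Stratum adjustment, closed form.** Replace SD by 15 × √(1−R²) and use 76 degrees of freedom. R² of 0.05, 0.10 and 0.20 gives 5.44, 5.30 and 5.00. The equivalent unadjusted size per arm is 40/(1−R²) = 42.1, 44.4 and 50.0.

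**3. Stratum adjustment, simulated with attrition.** 120 randomised in permuted blocks of 2, 4 or 6 within strata of 30/35/35%, 80 retained at random, equally spaced stratum means, total SD 15, 10,000 trials per scenario.

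| Assumed R² | 0 | 0.05 | 0.10 | 0.20 |
|---|---|---|---|---|
| Half-width, t-interval | 5.58 | 5.58 | 5.58 | 5.58 |
| Half-width, adjusted | 5.60 | 5.46 | 5.32 | 5.01 |
| Excludes zero at 6 points, t-test | 55% | 55% | 55% | 55% |
| Excludes zero at 6 points, adjusted | 55% | 57% | 58% | 63% |
| Actual size of nominal 10% t-test | 10.0% | 9.6% | 9.2% | 7.5% |

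The adjusted test has size 9.8–10.2% throughout. Strata of 20/20/60% change the half-widths by at most 0.02. With exact balance within strata (no attrition) the t-test is more conservative still: 8.4% at R² 0.10 and 6.6% at R² 0.20.

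**4. Which R² is plausible?** The smallest gap between extreme strata that yields a given R² is √(R² × 225 / (0.35 × 0.65)): 7.0, 9.9 and 14.1 points for R² 0.05, 0.10 and 0.20. With equally spaced means it is about 8, 12 and 17 points. Protocol 1.5.2 points both ways: brain delay is greatest in the most complex defects, but TGA and HLHS do not differ significantly in maturation scores. Low R² is the safer expectation.

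**5. The non-parametric branch (item 2).** Chance of a significant result at a 6-point shift, for R² 0/0.05/0.10/0.20:
- Normal data: van Elteren 52/54/56/60%, Wilcoxon 54/53/53/54%.
- Left-skewed data (assumed reversed-gamma residual, shape 1.5): van Elteren 72/74/77/79%, Wilcoxon 73/70/68/63%.

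Van Elteren size is 9.6–10.4%.

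**6. TMS with the fetal baseline.** Unadjusted: t(0.95, 118) × 1.32 × √(2/60) = 0.40. (The text of protocol 6.4 gives 0.44 for 60 per arm, which is the value for 50 per arm; Table 1 prints 0.40 for 50. The two appear swapped.) In simulation with stratum, fetal score and gestational age at scan in the model, and stratum R² set to 0, the half-width is 0.38/0.36/0.32 at correlations of 0.3/0.45/0.6. With 20% of baseline scans unusable it is 0.39/0.37/0.34. At zero correlation it is about 1% wider than unadjusted.

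**The case against.** The plan is not wrong. The t-test is the protocol's pre-specified method, Table 1 is built on it, and the recommended model will be reported anyway under item 3, with a fuller one under item 7. Both models target the same mean difference, so readers will have both estimates.

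The gain is also assumed and small. At R² 0.05 and 0.10, simulation gives the same significance decision from both analyses in 95% and 93% of trials at a 6-point effect. At R² 0.05 the adjusted interval is the wider one in about a quarter of trials. The van Elteren test loses about 2 percentage points if the strata carry no information. Replacing a primary analysis in a SAP dated 2022, when the statistical analyst was not blinded, invites suspicion.

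The fetal MRI proposal rests on unknown correlations. The post-natal score has a component the fetal score lacks (protocol 5.2.5), and protocol 1.5.2 places the CHD delay in late gestation, after the baseline scan, although protocol 1.4 describes the lag as occurring in the period when therapy starts. Item 7's covariate list may not be exhaustive.

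Most of this stands as a limit on size. It does not remove the asymmetry: very little is lost if the strata are uninformative, and precision is gained if they are not. The blinding point governs when and by whom the change is approved. An open-ended covariate list in a supplementary model does not commit anyone to using the fetal baseline.

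**Conclusion.** The point holds as a worthwhile improvement, not a defect. For Motor the likely gain is 0.1–0.3 points on a half-width of 5.58 (R² 0.05–0.10). It reaches about 0.6 points, equivalent to 50 infants per arm in place of 40, only if diagnosis explains 20% of the variance. If the strata are uninformative, the Motor interval is about 0.5% wider. For TMS the gain could be larger, up to a fifth of the half-width at a correlation of 0.6. All gains depend on an R² or a correlation that the documents do not supply. The conclusion that the t-test is valid but potentially conservative does not depend on a particular value.

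**What to change.** 1. Make the item 3 linear model (arm plus the three-level CHD stratum as randomised) the primary Motor analysis, reporting the adjusted difference, 90% interval and test. Keep the two-sample t-test as the sensitivity analysis.
2. Use the same model for Cognitive, Language, TMS and brain volumes. Do not extend it to adherence or to the WMI and PVL volumes, which have a peak at zero.
3. If normality fails, use the same model on a transformed score or a van Elteren test by stratum, and still report the adjusted mean difference.
4. For TMS and brain volumes only, add the baseline fetal value (maturation score or matching volume) and gestational age at that scan. Enter it as a covariate, not a change score, because the two scores are not on the same scale. Off-site drug initiation is allowed (protocol 4.1.2), so use only scans confirmed as taken before the first dose, with a missing-indicator otherwise. Do not adjust for postmenstrual age at the post-natal scan, since treatment may change the timing of birth.

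**Cost.** A dated change to SAP items 1–4 and matching text in the protocol synopsis and 6.3.2, as an amendment or documented deviation. Table 1 can stay as the unadjusted planning figure. No new data are needed and the Motor model spends two degrees of freedom. If neither stratum nor fetal score is prognostic, the TMS interval is about 1% wider, or 1.3% with 20% of scans unusable. The blinded investigators should approve the change before any results by arm are seen; a later switch would cost more in credibility than it gains in precision.
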